2. LIST OF ABBREVIATIONS

| Term | Definition / description |
|-------------|---|
| ADA | Anti-drug antibodies |
| AE | Adverse Event |
| AESI | Adverse Event of Special Interest |
| ALT | Alanine aminotransferase (SGPT) |
| ANCOVA | Analysis of covariance |
| AP | Alkaline phosphatase |
| APRI | AST to Platelet Ratio Index |
| AST | Aspartate aminotransferase (SGOT) |
| ATC | Anatomical Therapeutic Chemical |
| BI | Boehringer Ingelheim |
| BMI | Body Mass Index |
| BP | Blood pressure |
| CAP | Control Attenuation Parameter |
| CI | Confidence interval |
| CLDQ | Chronic Liver Disease Questionnaire |
| C-SSRS | Columbia – Suicide Severity Rating Scale |
| CTX-III | C-terminal crosslinked telopeptide of type III collagen |
| eCRF | electronic Case report form |
| CTC | Common Terminology Criteria |
| CTP | Clinical Trial Protocol |
| CTR | Clinical Trial Report |
| CV | Arithmetic coefficient of variation |
| DBL | Database Lock |
| DMC | Data Monitoring Committee |
| DTA | Data Transfer Agreement |
| ECG | Electrocardiogram |
| EDMS | Electronic Document Management System |
| eGFR | Estimated Glomerular Filtration Rate |
| ELF | Enhanced Liver Fibrosis |
| EOT | End of treatment |

| Term | Definition / description |
|----------|--|
| EQ-5D 5L | European Quality of Life Questionnaire – 5 Dimensions 5 Levels |
| FAS | Full Analysis Set |
| FFA | Free Fatty Acids |
| FGF-21 | Fibroblast Growth Factor 21 |
| Fib-4 | Fibrosis-4 index |
| GGT | Gamma-glutamyl transferase |
| HDL | High Density Lipoprotein |
| HMW | High Molecular Weight |
| HR | Heart rate |
| ICH | International Conference on Harmonisation |
| IPD | Important protocol deviation |
| IRT | Interactive Response Technology |
| iSAT | Independent safety analysis team |
| iSTAT | Independent statistician |
| LDL | Low Density Lipoprotein |
| LLOQ | Lower Limit of Quantification |
| MAR | Missing at random |
| MCP-Mod | Multiple Comparison Procedures and Modelling |
| MedDRA | Medical Dictionary for Regulatory Activities |
| mg | milligram |
| MMRM | Mixed model for repeated measures |
| MNAR | Missing not at random |
| MRI-PDF | Magnetic Resonance Imaging - Proton Density Fat Fraction |
| NA | Not applicable |
| NAb | Neutralising antibodies |
| NAFLD | Non-Alcoholic Fatty Liver Disease |
| NAS | NAFLD Activity Score |
| NASH | Non-Alcoholic SteatoHepatitis |
| PD | Protocol deviation |
| PK | Pharmacokinetics |
| PPS | Per protocol set |
| PRO | Patient Reported Outcome |

| Term | Definition / description |
|--------|--|
| Pro-C3 | N-terminal propeptide of type III collagen |
| PT | Preferred term |
| Q1 | Lower quartile |
| Q3 | Upper quartile |
| REP | Residual effect period |
| SAP | Statistical analysis plan |
| SD | Standard deviation |
| SOC | System organ class |
| TMF | Trial Master File |
| TS | Treated Set |
| UACR | Urine albumin/creatinine ratio |
| ULN | Upper limit of normal |
| ULOQ | Upper Limit of Quantification |
| VLDL | Very Low Density Lipoprotein |
| WHO | World Health Organisation |

3. INTRODUCTION

As per ICH E9, the purpose of this document is to provide a more technical and detailed elaboration of the principal features of the analysis described in the protocol, and to include detailed procedures for executing the statistical analysis of the primary and secondary variables and other data.

This TSAP assumes familiarity with the Clinical Trial Protocol (CTP), including Protocol Amendments. In particular, the TSAP is based on the planned analysis specification as written in CTP Section 7 “Statistical Methods and Determination of Sample Size”. Therefore, TSAP readers may consult the CTP for more background information on the study, e.g., on study objectives, study design and population, treatments, definition of measurements and variables, planning of sample size, randomisation.

This document describes the main analysis of study 1404-0043. One interim analysis was planned. This was described in a separate interim statistical analysis plan, and is not addressed further in this document. The interim analysis results were not intended to be used to stop the trial (which continued without modification after the interim analysis was performed), nor to make confirmatory claims. No statistical adjustments to Type 1 error are therefore considered necessary.

This TSAP is based on the 1404-0043 CTP (Version 6.0, 27JUL2023), together with the latest versions of the eCRF and relevant Data Transfer Agreements (DTAs) for external vendor data. The local protocol amendment for China (Version 1.0, 20APR2022) is also relevant to TSAP details regarding handling of biopsy data.

All statistical analyses defined in this TSAP will be performed by the trial statistician (TSTAT) with support from other trial team members following unblinding of the trial at final database lock (DBL). This TSAP will be finalized and signed prior to final DBL.

A DBL meeting will be held prior to taking the final database snapshot. It will be decided at this meeting whether any open cleaning issues will be accepted or not. Important protocol deviations (IPDs) will also be finalized prior to final DBL.

SAS[®] version 9.4 or later will be used for all analysis. Where statistical analyses require the use of R instead of SAS[®], R version 4.0.1 or later will be used.

The analyses and outputs specified in this TSAP will be included in the clinical trial report (CTR) unless specified otherwise.

4. CHANGES IN THE PLANNED ANALYSIS OF THE STUDY

The CTP also defined a Full Analysis Set (FAS) for efficacy analyses, which was defined in exactly the same way in the CTP as the Treated Set (TS) for safety analyses, i.e. both were defined as all randomized and treated patients. Reference to only the TS is retained in this document; the TS will be used for all efficacy and safety analyses.

5. ENDPOINTS

5.1 PRIMARY ENDPOINT(S)

The primary endpoint is the improvement (yes/no) from baseline in histological findings based on liver biopsy after 48 weeks of treatment. In practice, patients who discontinued treatment early but after 40 weeks of treatment are expected to have a post-baseline liver biopsy performed, and will also contribute to the primary endpoint derivation.

Patients are expected to have $NAS \geq 4$ and a fibrosis stage of F1a, F1b, F1c, F2 or F3 at baseline, according to the entry criteria for the trial.

Improvement in histological findings is defined as a composite of:

1. Improvement in NASH:
 - Decrease of at least 2 points in NAS, with at least 1 point decrease in NAS sub-score of either lobular inflammation or ballooning,

and

2. No worsening of fibrosis
 - Absence of any increase in fibrosis stage.

The NAS and fibrosis scoring system is summarized below. Details of the meaning of each grade/stage are referred to the CTP.

Table 5.1: 1 NAS scoring system for liver biopsies

| | Steatosis | Lobular Inflammation | Ballooning | NAS (Total Score) |
|--------------|------------------|-----------------------------|-------------------|--------------------------|
| | Grade 0 | Grade 0 | Grade 0 | |
| | Grade 1 | Grade 1 | Grade 1 | |
| | Grade 2 | Grade 2 | Grade 2 | |
| | Grade 3 | Grade 3 | | |
| Range | 0-3 | 0-3 | 0-2 | 0-8 |

The total score for NAS is the sum of the 3 NAS sub-scores for steatosis, lobular inflammation and ballooning respectively.

Table 5.1: 2 Fibrosis staging for liver biopsies

| | Fibrosis stage | Fibrosis score |
|--------------|-----------------------|-----------------------|
| | Stage F0 | 0 |
| | Stage F1a | 1 |
| | Stage F1b | 1 |
| | Stage F1c | 1 |
| | Stage F2 | 2 |
| | Stage F3 | 3 |
| | Stage F4 | 4 |
| Range | | 0-4 |

The fibrosis score is the same as the assigned stage of fibrosis without the distinction whether a stage of F1a, F1b or F1c was recorded (for a fibrosis score of 1). A patient who has a baseline fibrosis stage of F1a, F1b or F1c and a different post-baseline fibrosis stage of F1a, F1b or F1c is not considered to have worsening or improvement in fibrosis.

Central pathology readings of biopsy slides will be used. These will be physical central pathology readings for patients at sites in all countries, except in China where digital central pathology readings will be used for baseline in the primary endpoint definition (see further below).

All central pathology readings on the database which are considered adequate will be used, including any readings which may be performed by the back-up reader instead of the primary reader. An adequate liver biopsy reading means that the central pathology reader is able to fully read the slides provided (2 different types of staining; 1 per slide), and consequently provide values for all of the 3 NAS sub-scores and for the fibrosis stage, using the CTP guidance on scoring/staging. An inadequate liver biopsy reading will be completely re-read using at least one new stained slide, even if it could be partially read at the first attempt. Consequently, only adequate readings are expected to contribute data for analysis, and missing data at the level of individual items is not expected. In practice, any data records which are not labelled as inadequate on the database will be assumed to be adequate.

For baseline biopsy, either a biopsy performed during the screening period or a historical biopsy (within 6 months) will be used to provide baseline data, without any further distinction made for analysis purposes between these two situations.

For patients at sites in China, a single physical central pathology reading of the screening biopsy is expected to be available as part of the batch reading (screening reading 2). This will

not be used for baseline, since it may generate baseline values which are outside the ranges defined by the entry criteria, which may in turn create further issues with applying endpoint derivations and statistical models. Therefore, for patients at sites in China, the digital central pathology reading of the screening biopsy (screening reading 1) will be used as baseline. The potential limitations of using a digital baseline reading versus a physical post-baseline reading for primary endpoint purposes in China are acknowledged here. For patients at sites outside China, two physical central pathology readings of the same screening biopsy are expected to be available. The first of these (i.e. as used to assess eligibility) will be used for baseline (screening reading 1).

All available post-baseline biopsy data from physical central pathology reading will be used in the primary endpoint definition, with no restriction on how long the biopsy was done after the end of treatment, and using all available post-baseline biopsy results from patients who discontinued treatment early (including any results done earlier than Week 40, in the unlikely event that this situation exists). Patients without a post-baseline biopsy will be imputed as non-responders, regardless of whether a biopsy result was expected or not.

5.2 SECONDARY ENDPOINT(S)

5.2.1 Key secondary endpoint(s)

There are no key secondary endpoints defined in this trial.

5.2.2 Secondary endpoint(s)

Secondary endpoints are defined as follows:

MRI-PDFF

- Improvement in liver fat content (yes/no), defined as a percentage reduction of at least 30% from baseline in liver fat content, measured in units of % using MRI-PDFF, after 48 weeks of treatment.

Liver fat content (mean PDFF) in % is defined as the simple (unweighted) arithmetic mean of values from each of 9 liver segments obtained from a technically acceptable image reading. The mean will be calculated by the vendor and provided in the data transfer. If fewer than 9 liver segments can be read, the mean value will still be calculated, provided that 3 or more liver segments can be read. If fewer than 3 liver segments can be read, the mean will not be calculated and liver fat content (mean PDFF) is then expected to be missing. All non-missing values of liver fat content will be used for analysis, including those values derived from 3-8 liver segments.

Patients with MRI-PDFF data within the Week 48 visit window (see [Section 6.7](#)) who meet the above criterion are defined as responders, with no restriction on how long the MRI was done after the end of treatment, and non-responders otherwise. Patients without MRI-PDFF data within the Week 48 visit window will be imputed as non-responders in the main analysis of this endpoint [REDACTED]

- Absolute change from baseline in liver fat content, measured in units of % using MRI-PDFF, after 48 weeks of treatment.
- Percentage change from baseline in liver fat content, measured in units of % using MRI-PDFF, after 48 weeks of treatment.

Liver biopsy

- Improvement in fibrosis (yes/no), defined as at least one stage decrease in fibrosis stage from baseline, assessed by liver biopsy, after 48 weeks of treatment.
- Absolute change from baseline in total score for NAS, assessed by liver biopsy, after 48 weeks of treatment.

[figure not shown]
Central pathology biopsy data selection and derivation will be similar to what is described for the primary endpoint in [Section 5.1](#).

All available post-baseline biopsy data will be used in the secondary endpoint definitions with no restriction on how long the biopsy was done after the end of treatment, and using all available post-baseline biopsy results from patients who discontinued treatment early (including any results done earlier than Week 40).

For the responder endpoint, patients without a post-baseline biopsy will be imputed as non-responders, regardless of whether a biopsy result was expected or not.

5.4 OTHER VARIABLE(S)

5.4.1 Safety

Safety will be assessed based on:

- Adverse events
 - Routine reporting using the Medical Dictionary for Regulatory Agencies (MedDRA) coding dictionary (version in force at final DBL)
 - Adverse events of special interest (AESIs)
 - Adjudicated adverse events
- Laboratory variables
 - Specific laboratory tests are listed in CTP Table 5.2.3: 1
- Vital signs
 - Pulse rate
 - Systolic blood pressure
 - Diastolic blood pressure

- 12-lead ECG

Further details regarding 12-lead ECG derivations are given below.

- Columbia - Suicide Severity Rating Scale (C-SSRS)

Laboratory data

Estimated glomerular filtration rate (eGFR) and urine albumin/creatinine ratio (UACR) will be used as provided by the central laboratory, i.e. it will not be re-derived for analysis.

Fib-4 index and APRI will also be used as provided by the central laboratory.

12-lead ECG

Single digital ECG recordings are planned to be collected at each relevant visit with the exception of screening, where triplicate ECG recordings are planned. Each of the recorded single ECGs will then be evaluated for cardiac intervals, which comprise the RR, PR and QT interval and the QRS duration. Measurements of these intervals will be made on four cardiac cycles from the lead chosen (details not specified here).

The measurements of the cardiac cycles will be stored in the database, i.e. four values per visit (for a single ECG). The four cardiac cycles (or however many available) will be averaged, to give a single mean value for each visit. This will be done prior to the calculation below of the heart rate (HR) and heart rate corrected QT interval (QTc).

For screening only, where a triplicate ECG is expected, the mean values obtained for each single ECG will be further averaged across the 3 ECGs (or however many available) to give a single mean value for each variable at screening.

The heart rate will be derived from the RR interval as:

$$\text{HR [beats/min]} = \frac{60\,000}{\overline{RR}}$$

where \overline{RR} is the mean of the four RR intervals (measured in msec).

The QT interval corrected for HR according to Fridericia's formula (QTcF) for a single ECG will be derived as:

$$\overline{QTcF} [\text{msec}] = \left(\frac{1000}{\overline{RR}} \right)^{1/3} * \overline{QT} [\text{msec}],$$

[figure not shown]
where \overline{QT} is the mean of the four QT intervals and \overline{RR} is the mean of the corresponding preceding RR intervals of the four cardiac cycles for this ECG.

Likewise, the HR-corrected QT interval according to Bazett's formula (QTcB) for a single ECG is given by

$$\overline{QTcB} [\text{msec}] = \left(\frac{1000}{\overline{RR}} \right)^{1/2} * \overline{QT} [\text{msec}].$$

In the case that more than one ECG is available (i.e. more than one group of cardiac cycles) at a visit where a single ECG was planned, then the (first) ECG on that day which is not labelled as "UNSCHEDULED" will be used, regardless of the reason for this.

New onsets for categorical endpoints are derived based on the tables below:

5.4.2 Demographic and other baseline characteristics

Standard demographic variables and baseline characteristics are used as recorded on the eCRF.

The NAS and fibrosis scoring system is summarised in [Section 5.1](#).

Baseline definitions are given in [Section 6.7](#).

Time since NASH diagnosis will be calculated relative to randomisation date, not relative to informed consent date, since some investigators may only have considered the diagnosis to be confirmed after the screening biopsy was taken.

5.4.3 Treatment exposure and compliance

Treatment exposure is defined as the number of days from the first dose of study treatment to the last dose of study treatment inclusive. Any intermediate gaps in treatment in which the patient did not take medication will not be considered. It is assumed that an End of Treatment eCRF page will be available and complete for all treated patients at DBL, and that no special rules are needed to handle any missing information here.

Treatment exposure duration will be categorized as follows:

<4 weeks; 4-<8 weeks; 8-<12 weeks; 12-<16 weeks; 16-<20 weeks; 20-<24 weeks, 24-<28 weeks; 28-<32 weeks; 32-<36 weeks; 36-<40 weeks; 40-<44 weeks; 44-<48 weeks; \geq 48 weeks.

Study duration (regardless of whether on-treatment) will also use the same category definitions, although significant off-treatment follow-up after stopping treatment is not expected in this trial.

No treatment compliance calculations will be performed for analysis purposes based on return of unused and empty syringes. Any discrepancies between medication assigned, medication dispensed and medication administered will be assessed through the process for determining IPDs.

5.4.5 Immunogenicity variables

Immunogenicity will be evaluated using anti-drug antibodies (ADA) and neutralising antibodies (NAb). Only ADA is expected to be available for the CTR.

6. GENERAL ANALYSIS DEFINITIONS

6.1 TREATMENT(S)

6.1.1 Study Phases

The following summarises the study phases defined in the protocol for a patient who completes all visits and remains on treatment as planned:

Table 6.1.1: 1 Study phases

| Study Phase Description | Start | End |
|-----------------------------------|------------------------------|--|
| Screening phase | Date of informed consent | Day before Visit 2 (Week 0) |
| Treatment phase – dose escalation | Date of Visit 2 (Week 0)* | Day before Visit 26 (Week 24) |
| Treatment phase – maintenance | Date of Visit 26 (Week 24) | Date of Visit 32 (Week 48) |
| Follow-up phase | Day after Visit 32 (Week 48) | Date of end of study participation (expected to be 4 weeks after Visit 32 (Week 48)) |

* See also baseline definitions in [Section 6.7](#).

Patients who discontinue treatment early are not required or expected to complete the planned treatment phase. The follow-up phase is defined in the protocol as up to 4 weeks after the end of the planned treatment phase for patients who completed treatment, or 4 weeks after the End of Treatment visit for patients who discontinued early. It is not therefore expected that there will be a significant amount of data captured in this trial for any patients which is more than about a month after stopping treatment.

The follow-up period will not exist for any randomised patient who was lost to follow-up whilst still receiving treatment.

The definition of on-treatment for analysis purposes is given in [Section 6.1.6](#). The use of a residual effect period (REP) means that data captured during the follow-up period specified in the protocol could be assigned to the treatment period for analysis.

6.1.2 Planned Maintenance Treatment Group

Patients are randomised to one of four treatment groups (Placebo, Survodutide 2.4 mg, Survodutide 4.8 mg, Survodutide 6.0 mg). These are the planned maintenance treatment groups (weekly doses).

For the purposes of display in outputs, “planned treatment” means the same as “planned maintenance treatment”.

6.1.3 Actual Maintenance Treatment Group

According to the rules for escalating and adjusting the Survodutide dose given in the CTP, it is envisaged that some patients may not receive the planned maintenance treatment according to the randomised treatment group, whilst nevertheless remaining on treatment.

Actual maintenance treatment group will be defined for analysis as follows:

- If the patient started the maintenance period, then actual maintenance treatment group will be defined in all circumstances to be the dose at the start of the maintenance period (which is expected to be one of the Survodutide maintenance doses), regardless of whether previous dose escalation was performed in the expected way according to the protocol. This includes each of the following situations:
 - Any patient who successfully reached their planned maintenance dose at the end of the dose escalation period
 - Any patient who did not reach their planned maintenance dose at the end of the dose escalation period, and who only reached a lower maintenance dose
 - Any patient for whom the start and end maintenance dose are not the same, regardless of whether the patient started the maintenance period on their planned maintenance dose, and regardless of whether the permanent dose reduction was planned according to the protocol, or whether it was unplanned (e.g. where the wrong tolerability information was given to the IRT and the dose was not re-escalated back to correct the error).
- If the patient discontinued treatment during the dose escalation period, actual maintenance treatment group will be defined as the next planned maintenance dose up from the dose at discontinuation. The same rule will be applied irrespective of the reason for discontinuing treatment during the dose escalation period, and will be applied irrespective of whether the dose prior to the dose at discontinuation was as anticipated from the protocol dose escalation strategy.

Table 6.1.3: 1 Definition of actual maintenance treatment group for patients randomised to active Survodutide maintenance treatment who discontinued treatment during the dose escalation period

| Dose at discontinuation | Actual maintenance treatment group |
|---|------------------------------------|
| Dose = 0 mg | Placebo |
| $0.3 \text{ mg} \leq \text{Dose} \leq 2.4 \text{ mg}$ | 2.4 mg |
| $2.4 \text{ mg} < \text{Dose} \leq 4.8 \text{ mg}$ | 4.8 mg |
| Dose > 4.8 mg | 6.0 mg |

- All patients randomised to placebo maintenance treatment or who were switched to placebo during the dose escalation period will be assigned to placebo for actual maintenance treatment group.

For the purposes of display in outputs, “actual treatment” means the same as “actual maintenance treatment”.

The above rules cover all known and anticipated situations. The possibility of other situations which are not anticipated from the protocol, and which cannot be identified from blinded data, cannot however entirely be excluded. A review of unblinded dosing data will be performed immediately after unblinding the database at DBL, to identify any dosing situation for which the above TSAP rules might not be adequate. Such situations might include, but not necessarily be limited to, unexpected increases in maintenance dose, or starting Survodutide maintenance doses which are not one of 2.4 mg, 4.8 mg or 6.0 mg. An attempt will be made to find out whether data error or omission is the explanation, or whether a real issue actually occurred in any such patients. Any additional decisions required on assigning actual maintenance treatment at that time will be documented in the CTR.

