The NOAEL for BI 456906 in cynomolgus monkeys is only limited by the effect on body weight loss which reflects the pharmacology of the compound. Obviously, especially female monkeys with a profound lower initial body weight than male monkeys have to be considered oversensitive.

The lowest dose of 2.4 mg/ week in this trial is predicted to achieve sub-therapeutic PD response comparable to placebo in patients with NASH and fibrosis, however, still providing weight loss and improvement in the metabolic status.

The results from the 1404-0003 indicate that the most common GI adverse events such as nausea and vomiting occur at the beginning of the drug exposure and can be mitigated by a careful dose escalation. The tolerability of GLP-1 receptor agonists is known to improve over time, so is assumed that even higher doses of BI 456906 will be tolerated [[R20-0479](#)]. In addition, close monitoring is implemented in this trial to assure patients' safety.

Overall, the three selected maintenance doses are anticipated to support robust dose-exposure-response analyses for multiple safety and efficacy measures to serve as a basis for selection of the suitable dose regimen for the phase III trial.

Selected doses cover a safe starting dose of 0.3 mg/ week with different dose escalation schemes up to the target maintenance dose. The first 10 weeks of the dose escalation period will be identical for all three active treatment groups. The duration of the dose escalation up to the target maintenance dose differs among the active treatment groups from 14 to 22 weeks.

Dose adjustment will be allowed in all groups during the dose escalation period after Visit 14 as well as any time during the maintenance period based on the occurrence of AEs. If a patient does not tolerate a dose due to AEs in the previous two weeks and wishes to reduce the dose, then the dose should be decreased to the next lower tolerated target maintenance dose. The assignment of the lower dose will occur in a blinded fashion via IRT.

Examples:

- If a patient who does not tolerate a dose of 2.4 mg over two weeks during the dose escalation period and wishes to reduce the dose will be changed to placebo;
- If a patient who does not tolerate a dose of 3.6 mg over two weeks during the dose escalation period and wishes to reduce the dose will be changed to 2.4 mg;

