- If a patient who does not tolerate a dose of 4.8 mg over two weeks during the maintenance period and wishes to reduce the dose will be changed to 2.4 mg.

Dose adjustment should be done at the site. A patient is allowed to adjust the dose two times during the entire treatment period, once during the dose escalation and once during the maintenance period.

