6.1.5 Pooling Across Doses

In addition to specific Survodutide dose columns on descriptive summary tables, a combined column across doses (i.e. “All Survodutide”) will also be presented.

Combined Survodutide dose will not be used in any statistical models or descriptive summaries of efficacy.

Combined Survodutide dose will be included on all disposition and demographic/baseline summary tables, and in descriptive summaries of treatment exposure and safety.

Where a short treatment label is required on outputs, “Survo X.X mg” and “All Survo” will be used for the specific dose groups, and the combination across dose groups, respectively.

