6.1.6 Definition of On-Treatment

There is no continued study participation for patients who have discontinued treatment early. Consequently off-treatment data capture is expected to be restricted to those data captured during the safety follow-up period specified by the CTP, although there may be occasional unplanned exceptions to this.

Even for patients who completed treatment according to the protocol, data captured during the follow-up period may be relevant for safety.

It is important to be clear whether all available data will be used in a particular summary or analysis, or whether only on-treatment data will be used. The definition of “on-treatment” for this purpose is as described below, and it includes any temporary treatment interruptions which might occur prior to last dose of study treatment. It is assumed that all patients will have a date of last administration of study medication accurately recorded on the End of Treatment eCRF page.

“Off-treatment” refers to data which are captured after baseline but which are not “on-treatment” as defined below.

Safety

An AE start date or other safety assessment date will be considered “on-treatment” if the AE start date or assessment date is between the date of first dose and 28 days after the date of last

dose of study treatment inclusive (the residual effect period (REP) is defined as 28 days in this trial).

The same on-treatment definition will be used for all types of safety data.

Efficacy

All post-baseline efficacy data (including for exploratory biomarkers) will use the same 28-day definition of “on-treatment” as for safety, where on-treatment analyses are specified (as opposed to those efficacy analyses which use all data, both on- and off-treatment).

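### In the actual-treatment safety tables, 2.4 mg-arm patients switched to placebo during escalation are counted under placebo together with their on-survodutide events and exposure

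*SAP*

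**What the plan says.** SAP 6.1.3 defines actual maintenance treatment by three rules.

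- Patient started maintenance: "actual maintenance treatment group will be defined in all circumstances to be the dose at the start of the maintenance period".
- Patient stopped during escalation: "actual maintenance treatment group will be defined as the next planned maintenance dose up from the dose at discontinuation". Table 6.1.3:1 sends 0.3 to 2.4 mg to the 2.4 mg group, above 2.4 and up to 4.8 mg to the 4.8 mg group, and anything higher to 6.0 mg.
- Patients randomised to placebo, and those "who were switched to placebo during the dose escalation period will be assigned to placebo for actual maintenance treatment group".

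The route to placebo is in Protocol 4.1.2: a patient who does not tolerate 2.4 mg "during the dose escalation period and wishes to reduce the dose will be changed to placebo". Two adjustments are allowed, "once during the dose escalation and once during the maintenance period". In escalation they can be made only at Visits 16, 18, 20, 22 and 24.

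Under SAP 6.1.6 a safety record is on-treatment if the "AE start date or assessment date is between the date of first dose and 28 days after the date of last" dose; the dose level being taken plays no part. On the pooled column, SAP 6.1.5 says: "Combined Survodutide dose will be included on all disposition and demographic/baseline summary tables, and in descriptive summaries of treatment exposure and safety". SAP 7.7 and 7.8 give the main exposure summaries and all safety summaries by both actual and planned treatment. Protocol 7.2.5 names actual treatment as the safety grouping and adds randomised treatment for key analyses.

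**The concern.** A patient who took survodutide for at least 14 weeks, and was moved to placebo because of adverse events, is tabulated as if placebo had been the treatment throughout. The placebo column is the reference for every dose, so drug events and drug time placed there understate the difference from placebo, and the pooled active column loses patients selected for poor tolerability. SAP 7.4.1 lists tolerability and safety among the inputs to the Phase 3 dose choice, so these tables will be read for that purpose.

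**Working it through.** The plan gives no figure for this, so there is none to reproduce. The check applies the SAP rules to the escalation schedule (Protocol Table 4.1.4:1), with 60 patients per arm.

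**1. Who can be switched to placebo in escalation.** The dose at the two visits before each permitted adjustment, with the next lower target dose in parentheses:

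| Arm | V16 | V18 | V20 | V22 | V24 |
|---|---|---|---|---|---|
| 2.4 mg | 2.1 (placebo) | 2.4 (placebo) | 2.4 (placebo) | 2.4 (placebo) | 2.4 (placebo) |
| 4.8 mg | 3.0 (2.4) | 3.6 (2.4) | 4.2 (2.4) | 4.8 (2.4) | 4.8 (2.4) |
| 6.0 mg | 3.0 (2.4) | 3.6 (2.4) | 4.2 (2.4) | 4.8 (2.4) | 5.4 (4.8) |

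With one adjustment allowed in escalation, only the 2.4 mg arm can reach placebo. A switch to placebo during maintenance does not move the patient, because the dose at the start of maintenance decides.

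**2. Survodutide received before the switch.** Visits 2 to 15 give 14 scheduled doses. Protocol 4.1.4 allows two single missed doses in escalation: 14 − 2 = 12. Visit 16 is Day 99 and Visit 24 is Day 155:
- 99 − 1 = 98 days; 98/365.25 = 0.27 years
- 155 − 1 = 154 days; 154/365.25 = 0.42 years

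**3. Where events and time go.** Events since the first dose follow the patient to the placebo column. The 98 to 154 days enter placebo exposure (SAP 7.7). In the exposure-adjusted table (SAP 7.8.1) time at risk stops at the first onset of the event concerned. The full 98 to 154 days therefore count only for events with no onset before the switch; for the events that led to it, the time ends earlier.

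**4. Share of the placebo column.** k switched patients form k/(60 + k); k is assumed.
- k = 1: 1/61 = 1.6%
- k = 3: 3/63 = 4.8%
- k = 6: 6/66 = 9.1%

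The four unequal-allocation scenarios in Protocol 7.5 all keep placebo at 60, so none covers such a switch.

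**5. Illustration of the effect.** Take the nausea rates from the multiple rising dose trial in Protocol 1.2 (23% placebo, up to 70% on drug), and assume every switched patient had nausea on drug. Placebo = (60 × 0.23 + k)/(60 + k); All Survodutide = (180 × 0.70 − k)/(180 − k).

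| k | Placebo | All Survodutide | Difference (points) |
|---|---|---|---|
| 0 (as planned) | 23.0% | 70.0% | 47.0 |
| 1 | 24.3% | 69.8% | 45.6 |
| 3 | 26.7% | 69.5% | 42.8 |
| 6 | 30.0% | 69.0% | 39.0 |

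This is not a forecast; that trial used other escalation schemes over 6 weeks.

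**6. Early stops, relevant to the choice of version.** "The first 10 weeks of the dose escalation period will be identical for all three active treatment groups", and every dose at Visits 2 to 13 is 2.4 mg or less in all active arms. Stops at those visits therefore all count under 2.4 mg. If 6 of 60 stopped then in each active arm (assumed), planned rates of 10% in each arm become (3 × 6)/(60 + 2 × 6) = 18/72 = 25.0% at 2.4 mg, and 0/54 for these stops in each higher group.

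**The case against.** The strongest reply is that the plan already contains the remedy. SAP 7.8 produces every safety table by planned treatment too, including the registry tables in 7.8.1, and SAP 7.7 does the same for the main exposure summaries. There a switched patient stays under 2.4 mg and in All Survodutide. A planned-versus-actual shift table shows the reassignments. Disposition with stop reasons, the Kaplan-Meier plot and early-discontinuer exposure use planned treatment. No safety hypothesis is tested, and few patients may be switched. All of this stands, and it limits the consequence. It does not make the actual-treatment placebo column correct. The split of some tables into escalation and maintenance does not help either, because the patient stays in the same column; the worst-grade and exposure-adjusted tables specify no split.

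Three stronger readings are tempting and are not supported.

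- *The safety reporting as a whole is distorted.* Only the actual-treatment version is affected, and the SAP ranks neither version above the other.
- *The reassignment of early stops reverses the dose order.* Counting a stopped patient at the next dose up is a pre-specified as-treated convention, shown beside the randomised view. Any effect on the order depends on stop rates that the documents do not give.
- *The registries will receive the affected version.* The visible SAP does not say which version is posted. That is mainly missing detail, and parts of the public copy are redacted or absent.

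**Conclusion.** The point holds for the actual-treatment safety and exposure tables and is minor. A stated rule places 2.4 mg-arm patients with 12 to 14 or more survodutide doses under placebo, with their on-drug events, and removes them from the pooled active column. The addition of 98 to 154 days per patient to placebo exposure follows from the visit schedule, assuming the switch takes effect at the scheduled visit. How many patients are affected is not documented, so the 1.6% to 9.1% share and the nausea figures are illustrations under assumed counts. The planned-treatment tables are untouched, so no information is lost.

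**What to change.** In the actual-treatment safety and exposure tables, show patients who received survodutide and were then switched to placebo in a separate column. If they are very few, use a footnote instead and exclude them and their events from the placebo column. Keep them in All Survodutide in either case.

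State in SAP 7.8 that the registry adverse event tables, and between-dose comparisons of adverse events leading to discontinuation, use planned treatment. The reason for the second is step 6: stops at Visits 2 to 13 from all active arms are counted under 2.4 mg in the actual-treatment version.

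The cost is SAP wording and one column or footnote. The planned-treatment tables and the shift table are already specified, so no new data are needed and no dosing rule changes. The drawback is that the extra column may hold very few patients.
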